2.0 Introduction, Background, and Rationale

2.1 Introduction

The Multidisciplinary Association for Psychedelic Studies (MAPS), a non-profit research and educational organization, is proposing a double-blind, randomized, placebo-controlled exploratory pilot study with dose escalation to assess safety and feasibility of 3,4-methylenedioxymethamphetamine (MDMA)-assisted therapy for social anxiety in 12 MDMA-naïve adults on the autism spectrum. This study will also obtain estimates of effect size based on response to two experimental sessions of MDMA-assisted therapy in comparison to an inactive placebo control group in order to properly power subsequent investigations. The study will be conducted in association with researchers at Los Angeles Biomedical Research Institute (Harbor-UCLA Medical Center, main site) and Stanford University Medical Center (collaborating site). The sponsor has ongoing studies using MDMA-assisted psychotherapy in the treatment of posttraumatic stress disorder (PTSD) that will be used to inform the safety and dosing aspects of this new investigation as a potential therapy for social anxiety that could benefit the quality of life of adults on the autism spectrum.

Based on the known effects of MDMA, as well as individual reports, the sponsor intends to conduct this exploratory study which will focus on enhancing functional skills and quality of life in this underserved population, who tend to experience greater anxiety, depression and victimization than typically developing (TD) adults. The exploratory elements of this study are: group sequential dosing, refinement of the treatment method, study endpoints, assessment of clinical response, appropriateness of the chosen measures, and biomarker analysis of response to treatment. This study is designed to explore treatment-related changes in social anxiety, social perception, and neuromodulators such as oxytocin (OT), arginine vasopressin (AVP) and cortisol (CORT), that are critically involved in anxiety and social behavior. Outcomes from this study, if promising, will inform the dose, endpoints and treatment regimen for subsequent studies.

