2.3 Protocol Purpose

This is a double-blind, randomized, placebo-controlled, dose-finding Phase 2 pilot study designed to explore the safety and the therapeutic potential of MDMA-assisted therapy for treating social anxiety in 12 MDMA-naïve adults on the autism spectrum. This study will provide an estimate of effect size based on response to two experimental sessions of MDMA-assisted therapy in autistic adults on measures of safety, social anxiety, social perception, and psychiatric symptoms in comparison to a placebo control group. The primary outcome measure for the study will be the clinician-administered Liebowitz Social Anxiety Scale (LSAS) administered by a blinded Independent Rater (IR). Self-report measures will correspond to indications that often co-present with autism, including anxiety, stress, depression, emotion regulation, alexithymia, differences in some empathy domains, and other psychosocial challenges. Subjects will receive ongoing social support during the study in the form of non-drug therapy and active involvement of a support partner.

This study will employ biomarker analyses in combination with clinical outcome measures to provide useful insights into the underlying mechanism of MDMA's psychosocial and anxiolytic effects, and to examine any biological differences to treatment responses. The time course of biomarker concentrations will be used to determine if MDMA-assisted therapy causes lasting changes in biomarker levels in comparison to baseline.

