3.0 Protocol Objectives

The main objective of this study is to collect safety data to examine whether MDMA-assisted therapy will be tolerated and to estimate effect size of symptom reduction in social anxiety that is common in the adult autistic population as evaluated by standard clinical measures.

3.1 Primary Objective:

To estimate effect sizes of social anxiety symptom reduction between MDMA and placebo, as measured by the clinician-administered LSAS administered by a blinded IR, at baseline, one day, two weeks, and one month after each experimental session, and at 6-month follow-up.

3.2 Secondary Objectives:

The following objectives will compare MDMA subjects to placebo subjects in Stage 1:

- To assess effects on levels of OT, AVP, and CORT in peripheral blood at baseline, once during each experimental session between hours 2 – 3, one month after the second experimental session, and at 6-month follow-up.
- To assess effects on social perception using The Awareness of Social Inference Test (TASIT) at baseline, once during each experimental session between hours 2 – 3, one month after the second experimental session, and at 6-month follow-up.
- To assess effects on emotion labeling using the Toronto Alexithymia Scale-20 (TAS-20) at baseline, one month after each experimental session, and 6-month follow-up.
- To assess effects on emotion regulation using the Emotion Regulation Questionnaire (ERQ) at baseline, one month after each experimental session, and 6-month follow-up.
- To assess effects on depression symptoms as measured by the Beck Depression Inventory-II (BDI-II) at baseline, one day, two weeks, one month after each

- experimental session, monthly by mail during the 5 months leading up to the 6-month follow-up assessment.
- To assess effects on perceptions of stress as measured by the Perceived Stress Scale (PSS) at baseline, within 24 hours after each experimental session, one month after each experimental session and monthly by mail leading up to the 6-month follow-up assessment.
 - To assess effects on four aspects of empathy, as measured by the Interpersonal Reactivity Index (IRI) at baseline, within 24 hours after each experimental session, one month after each experimental session, and at the 6-month follow-up assessment.

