4.2.1 Inclusion Criteria

Individuals eligible to be enrolled into this protocol are subjects who:

1. Be diagnosed with Autism Spectrum Disorder;
2. Have at least moderate to severe Anxiety;
3. Have had at least one unsuccessful attempt at treatment for PTSD either with talk therapy or with drugs, or discontinuing treatment because of inability to tolerate psychotherapy or drug therapy.
4. Are at least 21 years old;
5. Have completed two years of college-level education or comparable vocational training;
6. Must be generally healthy;
7. Must sign a medical release for the investigators to communicate directly with their therapist and doctors;
8. Are willing to refrain from taking any psychiatric medications during the study period;
9. Willing to follow restrictions and guidelines concerning consumption of food, beverages, and nicotine the night before and just prior to each experimental session;

10. Willing to remain overnight at the study site;
11. Agree to have transportation other than driving themselves home or to where they are staying after the integrative session on the day after the MDMA session;
12. Are willing to be contacted via telephone for all necessary telephone contacts;
13. Willing to give blood samples;
14. Must have a negative pregnancy test if able to bear children, and agree to use an effective form of birth control;
15. Must provide a contact in the event of a participant becoming suicidal;
16. Are proficient in speaking and reading English;
17. Agree to have all clinic visit sessions recorded to audio and video
18. Agree not to participate in any other interventional clinical trials during the duration of this study.

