2.0 Introduction

This document presents a Statistical Analysis Plan (SAP) for MAPS study protocol MAA-1, a Phase 2 pilot clinical trial designed to evaluate the safety, feasibility, and efficacy of MDMA-assisted psychotherapy in treating social anxiety in adults on the autism spectrum.

The Multidisciplinary Association for Psychedelic Studies (MAPS) is a non-profit research and educational organization working to obtain approval for the prescription use of 3,4-methylenedioxymethamphetamine (MDMA)-assisted psychotherapy in adults on the autism spectrum with social anxiety. This is an initial pilot study to assess the efficacy of MDMA for this indication, following promising results from MAPS-sponsored studies of MDMA-assisted psychotherapy for posttraumatic stress disorder (PTSD).

The Phase 2 pilot study will examine the safety, feasibility, and efficacy of MDMA-assisted psychotherapy for social anxiety in 12 MDMA-naïve adults on the autism spectrum. This study is designed as a dose escalation study to assist with the exploration of safety and finding the most effective dose in this population. Subjects assigned to the MDMA group will receive two of three different doses, either 75 mg, 100 mg, or 125 mg MDMA. Overall, eight subjects (66.7%) will be randomized to the MDMA group and four subjects (33.3%) will be randomized to the placebo group. Subjects who received the placebo during Stage 1 will have the opportunity to cross over and take part in a second study segment, referred to as Stage 2, with two open-label experimental sessions, after completing the six-month follow-up visit at the end of Stage 1.

This study is designed to obtain safety data, and secondarily estimates of effect size for efficacy. The data will be used to determine study design and dosing for future studies for this indication. MAA-1 is also intended to contribute to the development of a manualized psychotherapeutic approach to this potential treatment. This study is exploratory. As a result, the sponsor will perform tests on all statistical comparisons without correcting for multiple comparisons.

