3.0 Analysis Plan Objectives

3.1 Primary Objective

The primary objective is to assess changes in social anxiety symptoms between MDMA and placebo groups, as measured by the clinician-administered Liebowitz Social Anxiety Scale (LSAS) administered by a blinded Independent Rater (IR), at baseline, one day, two weeks, and one month after each experimental session, and at 6-month follow-up.

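### Inclusion criterion 3 requires a failed or untolerated treatment for PTSD, but the trial's stated population is autistic adults with social anxiety

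*Protocol*

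**What the plan says.** Criterion 3 in Protocol 4.2.1 has two branches. The first is "Have had at least one unsuccessful attempt at treatment for PTSD either with talk therapy or with drugs". The second is "or discontinuing treatment because of inability to tolerate psychotherapy or drug therapy", which names no condition.

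The criterion is not advisory. Protocol 4.2 requires all inclusion criteria to be met at baseline, 5.2.2 and 5.3 make this a condition of enrolment, and 5.2.3 has eligibility reviewed again before dosing.

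The indication is described differently everywhere else:

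- Protocol 2.1 presents "this new investigation as a potential therapy for social anxiety that could benefit the quality of life of adults on the autism spectrum".
- Protocol 2.3 sets out to explore "the therapeutic potential of MDMA-assisted therapy for treating social anxiety".
- Protocol 3.0 aims to estimate "symptom reduction in social anxiety that is common in the adult autistic population".
- SAP 2.0 describes "MDMA-assisted psychotherapy in treating social anxiety in adults on the autism spectrum", and SAP 4.0 gives the same population.
- SAP 3.1 states the primary objective as "to assess changes in social anxiety symptoms between MDMA and placebo groups".

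The only inclusion criterion about anxiety is criterion 2, "Have at least moderate to severe Anxiety", which does not say that the anxiety must be social.

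**The concern.** A binding entry rule names a disorder that the trial does not study. Two things can follow, and neither is harmless.

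If the rule is applied as written, the trial recruits a subset of the stated population defined by PTSD treatment or, on the wider reading, by past intolerance of therapy. Protocol 12.0 intends the estimated effect size to set the sample size of later studies, so those studies would be planned from people other than the ones described. Feasibility of recruitment, judged partly by enrolment rates, is also an objective (Protocol 3.2, SAP 3.2), and this rule acts directly on enrolment.

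If the rule is ignored, subjects enter who fail a written criterion. SAP 8.4 counts anyone enrolled but found not to meet the criteria as a major deviation and drops them from the per-protocol analyses.

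The issue is to whom the estimate applies. Randomisation takes place among whoever is enrolled, so the contrast between MDMA and placebo is not confounded.

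**Working it through.** No statistical calculation applies. The check compares the texts and counts where PTSD appears.

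**Step 1: where PTSD is named.** Abbreviation and reference lists are left out.

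| Section | What PTSD refers to |
|---|---|
| Protocol 2.1 | The sponsor's other studies |
| Protocol 2.2.4 | Use of MDMA in therapy before scheduling |
| Protocol 2.2.5 | Completed studies in PTSD |
| Protocol 2.3 | The dose with indications of efficacy in PTSD |
| Protocol 4.2.1 | **Entry to this trial (criterion 3)** |
| Protocol 6.5 | An earlier study that used the same drug supply |
| Protocol 7.2 | Reactions seen in earlier subjects |
| SAP 2.0 | Results of earlier sponsor studies |

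Of eight sections, seven concern other studies or earlier use and one applies PTSD to this trial's subjects. Protocol 2.2.1 lists trauma among conditions that often accompany autism, but it sets no requirement.

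**Step 2: does the trial's content concern PTSD?** SAP 7.1 lists LSAS, PSS, BDI-II, IRI, RSES, STAI, TASIT, TAS-20, ERQ and QoL-Q: ten measures, none for PTSD. Protocol 7.1 says that subjects will discuss social anxiety symptoms in therapy and assessments. No objective in Protocol 3.0 or SAP 3.0 mentions PTSD.

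**Step 3: who gets in under each reading of the second branch?** On the narrow reading, which is the natural one, the treatment stopped is the PTSD treatment of the first branch. On the wide reading it is any psychotherapy or drug therapy. For an autistic adult with social anxiety, considering criterion 3 alone:

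| Treatment history | Narrow | Wide |
|---|---|---|
| No previous treatment | Excluded | Excluded |
| Social anxiety treatment, tolerated but unsuccessful; no PTSD treatment | Excluded | Excluded |
| Social anxiety treatment stopped as intolerable; no PTSD treatment | Excluded | Eligible |
| Unsuccessful PTSD treatment | Eligible | Eligible |
| PTSD treatment stopped as intolerable | Eligible | Eligible |

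The wide reading changes one row. Under both readings the rule still shuts out people who fit the stated population, including those whose social anxiety treatment simply did not work.

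**Step 4: size.** The documents give no figure for how many autistic adults with social anxiety have had PTSD treatment or have stopped a therapy as intolerable. The share excluded therefore cannot be derived and is not estimated here. For scale only: allocation is 8 to 4 among 12 subjects (Protocol 5.3), so one placebo subject removed from the per-protocol set would be 1/4 = 25% of that arm.

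**The case against.** Nobody can easily defend the wording itself. The case on the other side is about weight.

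*The eligibility lists look condensed.* MDMA-naive status is mandatory in Protocol 4.2 but absent from 4.2.1. Hypertension (7.2.1) and bipolar or psychotic disorders (7.2.2) are said to be excluded, but 4.2.2 has only a general clause. Condensing explains missing detail, and for that reason the vagueness of criterion 2 is raised here only for clarity. It does not explain how a different disorder came to be named.

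*It is an obvious carry-over that any reader would see through.* That is plausible, given how consistently the rest of the text names social anxiety, but it is inference. Screeners and monitors work from the written criteria, and the protocol calls for them to be checked repeatedly. Actual screening practice cannot be seen, so the harm is conditional on the text being followed.

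*The second branch lets intended subjects in.* Protocol 2.2.1 says that medication often does not work in autistic people and that rapport problems hinder psychotherapy, so some might qualify on the wide reading. This softens the exclusion. It does not remove it, because an ineffective treatment is not the same as an intolerable one.

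*This is a 12-subject pilot without a power calculation (Protocol 12.1, SAP 6.0).* True, and the comparison stays valid for those enrolled. But the pilot's product is an effect size for planning, so the population behind it matters. As for the per-protocol consequence, the definition of a major deviation in SAP 8.4 is itself garbled, since it also sweeps in anyone who completes through the primary endpoint. The conclusion therefore does not rest on it.

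**Conclusion.** The concern holds, and the text must be corrected. Criterion 3 contradicts the population stated throughout the protocol and SAP, and neither reading of its second branch resolves the conflict. One of eight sections naming PTSD applies it to this trial's subjects, and none of ten outcome measures assesses it.

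The practical effect assumes that the criterion is enforced as written. Its extent also depends on how the second branch is read, and the proportion excluded is unknown. The damage is to applicability and recruitment; the randomised contrast is unaffected.

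Criterion 2 is a lesser matter. As worded it could admit people whose anxiety is not social, but it keeps out nobody intended. It is a point of clarity and adds nothing to the seriousness of this finding.

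**What to change.** Reconcile criterion 3 in Protocol 4.2.1 with Protocol 2.3 and SAP 2.0 and 4.0. Either remove the PTSD wording or, if the sponsor does want a prior-treatment requirement, make both branches refer to the condition under study. Whether to keep such a requirement is for the sponsor to decide.

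For clarity, name social anxiety in criterion 2 and refer to the LSAS that the independent rater already gives at screening (Protocol 5.2.1). Any threshold is left to the sponsor.

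The cost is an amendment to the eligibility text. No assessment is added, because the LSAS and the SCID are already part of screening.

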4.2.2 Exclusion Criteria

Individuals not eligible to be enrolled into this protocol are those who:

1. Are pregnant or nursing, or if a woman who can have children, those who are not practicing an effective means of birth control;
2. Weigh less than 48 kg;
3. Are abusing illegal drugs;
4. Are unable to give adequate informed consent;
5. Upon review of past and current drugs/medication must not be on or have taken a medication that is exclusionary.
6. Upon review of medical or psychiatric history must not have any current or past diagnosis that would be considered a risk to participation in the study.

5.0 Methods

5.1 Measures

The following diagnostic, outcome, safety, and process measures will be used in the study. All therapy sessions, including experimental sessions, may be recorded to audio and video, with all recordings preserved for research and training purposes.

5.1.1 Diagnostic Measures

The Autism Diagnostic Observation Schedule, Second Edition (ADOS-2, Module 4) is a semi-structured social interaction to assess autism and autism-spectrum disorders in adults [127]. It takes 40 to 60 minutes to administer ADOS-2 Module 4. The assessment includes a construction task, semi-structured conversation with the assessor, emotional and creative responses to cartoons and pictures, describing an unusual event and telling a story. The assessment is scored by an algorithm and assessment is made on observation of participant nonverbal and verbal behavior, restricted or stereotyped behavior and degree of empathy. Most factors of the original Module 4 were reliable, with kappa greater than 0.60 and inter-rater reliability was high, from 0.83 for “repetitive /restrictive” to 0.93 for “social” [127]. Subsequent specific examination of the measure found that Module 4 could reliably detect ASD in adults, and that it could differentiate between autism spectrum disorders, psychopathy and typical development [128]. The activities used in the ADOS-2 are identical to those used in the original version of the ADOS, but instructions have been revised. A certified assessor will administer the ADOS-2 at screening to confirm autistic status.

The Structured Clinical Interview for Diagnoses Axis 1 Research Version (SCID-I-RV) is a structured interview used to assess and diagnose psychiatric conditions listed in the DSM-IV [129]. The interview is designed for use in adults and is suitable for use with psychiatric and non-psychiatric populations. The SCID consists of ten modules. Modules are based upon the symptoms listed for diagnoses as set out in the DSM-IV. The SCID can take from 30 to 90 minutes to perform. The SCID will be used to assess for psychological disorders. The PI will administer the SCID once at screening.

5.1.2 Outcome Measures

The primary outcome measure for the study will be the clinician-administered LSAS [130]. The LSAS is a 24-item, semi-structured interview on the severity of Social Anxiety Disorder, which has been widely used in clinical studies, including research on social anxiety in autistic adults [16]. The LSAS separately assesses fear (0 to 3 = none, mild, moderate, severe) and avoidance (0 to 3 = never, occasionally, often, usually) of 24 social situations, providing an overall social anxiety severity rating and subscale scores for performance fear, performance avoidance, social fear, and social avoidance. The overall scores are interpreted as: 55-65 moderate, 65-80 marked, 80-95 severe, and greater than 95 very severe social anxiety. The LSAS has been shown to have good internal consistency (score inter-correlations ranging from 0.81 to 0.96), reliability, convergent validity with other measures of anxiety, and sensitivity to treatment response. The LSAS was also demonstrated to be sensitive to the effects of pharmacological

treatments of social phobia in comparison to placebo and to have convergent validity [15]. A qualified blinded IR, who will not be present during experimental sessions, will complete the LSAS assessment. Subjects will be instructed not to inform the IR of any beliefs they or others have concerning their condition assignment during the assessment.

The BDI-II is a 1996 revision of the BDI, a 21-item self-report measure [131, 132], that will serve as a measure of depression according to DSM-IV criteria [133]. The BDI-II has been validated, has high internal consistency and good test/re-test reliability, and is not overly sensitive to daily variations in mood. It takes five to ten minutes to complete [133]. Score cutoffs indicate: 0-13 minimal depression, 14-19 mild depression, 20-28 moderate depression, and 29-63 severe depression. Higher scores indicate more severe depressive symptoms. The BDI-II will be completed according to the Time and Events table.

The PSS is a 10-item self-report measure that is widely used in research to assess stress in persisting conditions and takes about 1 – 2 minutes to complete. The PSS includes six negative items that are intended to assess lack of control and negative affective reactions and four positive items that measure the degree of ability to cope with existing stressors. Individuals indicate how often they felt or thought a certain way during the last month (0 = *never*, 4 = *very often*). The PSS was correlated with depressive symptomatology and social anxiety in TD populations [134]. The PSS will be completed according to the Time and Events table.

The IRI assesses four aspects of empathy: social functioning, self-esteem, emotionality, and sensitivity to others [135-137]. Empathy is not a discrete emotion. More accurately, empathy is a set of constructs. Therefore, the IRI accounts for the fact that each construct concerns an individual's responses to the observed experiences of other people, yet each construct is distinctive from the others. The self-report questionnaire includes 28 items that are rated on a 5-point, Likert-type scale. The four 7-item subscales include two measures of cognitive empathy and two measures of affective empathy. The internal reliabilities for the four scales range from .71 to .77, and test-retest reliabilities range from .62 to .71 [135]. One study [138] administered the IRI to 21 adults with Asperger's Syndrome and to 21 matched controls. As anticipated, the Asperger's group scored lower on the measures of cognitive empathy, but they scored similarly to controls on the Empathic Concern scale, and scored higher than controls on the Personal Distress scale. In the absence of an abundance of robust validity testing of empathy assessments with adult autistic populations, the IRI provides a good option for a multidimensional assessment of empathy factors. The IRI will be completed according to the Time and Events table.

The RSES is widely used in clinical research to assess two facets of self-esteem: self-competence (instrumental value) and self liking (intrinsic value) [139]. The RSES is a simple, 10-item scale with five questions for each facet, and it can be completed in 1 – 2 minutes. In anecdotal accounts, autistic adults have reported increased self-esteem and self-competence following MDMA use, attributes that influence anxiety, affective states, and interpersonal style. The RSES satisfies tests of item convergent and discriminant

validity, internal consistency and reliability, and floor and ceiling effects [140]. Cronbach's α has been shown to be substantial ($M = 0.81$) across cultural contexts [140]. The RSES will be completed according to the Time and Events table.

The STAI Form Y is a widely used self-report instrument for assessing anxiety in adults that includes separate measures of state and trait anxiety [141, 142]. The STAI evaluates the essential qualities of feelings of apprehension, tension, nervousness, and worry. The STAI differentiates between the temporary condition of "state anxiety" and the more general and long-standing quality of "trait anxiety." The STAI state scale asks for feelings at the moment of filling out the questionnaire, and the STAI trait scale asks subjects to indicate how they generally view themselves. The proposed study will use the 20-item trait scale with questions about how respondents generally feel. Response options are based on a 4-point Likert-type scale (1=almost never, 2=sometimes, 3=often, 4=almost always). The STAI will be completed according to the Time and Events table.

The TASIT is an audio-visual test of social perception and emotional expression comprehension presented in video vignettes of interpersonal interactions [143]. Standardized response probes assess understanding of emotional expression. The 3-part test includes The Emotion Evaluation Test, the Social Inference-Minimal, and the Social Inference-Enriched test. Each part takes approximately 10 – 15 minutes to complete. The TASIT has demonstrated adequate test-retest reliability (range = 0.74 for "Emotional Evaluation" to 0.88 for "Social Inference - Minimal") and high internal consistency $\alpha = 0.71$ [144, 145]. The TASIT will be completed according to the Time and Events table.

The ERQ is a brief measure of self-reported emotion-regulation. It consists of ten items that is intended to assess means of coping with emotions via changing them, as through reappraisal, or suppressing them [146]. Respondents rate indicate the extent of their agreement or disagreement with each item by selecting a point on a 7-point Likert scale, where 1= strongly disagree and 7 = strongly agree. The ERQ should take four to six minutes to complete. Specific items are summed to produce two separate scales, Reappraisal and Suppression. The measure is reliable, with Reappraisal obtaining a Cronbach's alpha of 0.79 and Suppression an alpha of 0.73, and test-retest reliability of 0.69 [146], and scores on the ERQ are correlated with other measures of degree of emotional expressivity. Studies in people with Asperger's or ASD suggest difficulties with emotion regulation that include less use of reappraisal and greater numbers of negative versus positive emotions [147]. The ERQ will be completed according to the Time and Events table.

The TAS-20 is a 20-item measure of self-reported difficulties with recognizing and verbalizing emotions [148, 149]. Responses are made on a 5-point Likert scale where 1 = strongly disagree and 5 = strongly agree. Estimated time of measurement is 5 to 10 minutes. The scale is comprised of three subscales; Difficulty Describing Feelings, Difficulty Identifying Feelings and Externally-Oriented Thinking, with all scales summed to create a total score reflecting presence and degree of alexithymia. The TAS-20 can be used diagnostically with a score of 61 or higher indicative of alexithymia. The TAS-20 is reliable and has good test-retest reliability (Cronbach's alpha = 0.81, test-retest of 0.77).

It is an established measure of alexithymia. There is some suggestion of an overlap between this condition and Asperger's syndrome, with samples of people with Asperger's syndrome showing greater rates of alexithymia than age and gender-matched controls [147, 150]. The TAS-20 will be completed according to the Time and Events table.

The QoL-Q is a 40-item measure of quality of life. It is administered as an interview and assesses eight domains [151]. The QoL-Q assesses the following domains; self-determination, (autonomy and decision-making), social inclusion (acceptance by others within the community, supports), material well-being (financial security and socioeconomic status), personal development (education, skills and competence), emotional well-being (spirituality, happiness, sense of safety) interpersonal relations (intimacy, affection, friendship), rights (voting, privacy, legal rights and protections) and physical well-being (health, nutrition, mobility). It is estimated to take between a half hour to an hour to complete the QoL-Q. It can be used in diverse populations, including autistics and other developmentally disabled people [152, 153]. The measure has excellent internal reliability ($\alpha = 0.90$) and strong test-retest reliability ($\alpha = 0.87$). The QoL-Q will be completed according to the Time and Events table.

